There will be a total of three replications of the Automatic Oxygen Control System devices at each site. These three devices will be used under the supervision of a study engineer and/or healthcare provider.

There are no known difficulties in using the device.

The cost of the device is funded by the study.

Doctors, respiratory therapists, and nurses will be trained on how to use the device. They will receive training on how to turn the device off and on, switch between automatic and manual modes, and adjust the FiO2 settings on the device. This training will be conducted by the study personnel prior to placing the device on a patient. This training should take less than 5 minutes to complete. A member of the study personnel will be present at the infant's bedside during the first 12 hours of the study period the infant is attached to the device and then 1 hour daily to make sure the device is functioning properly. A member of the study team will also be on-call during the entire study period to answer questions about the device.

The study device will not be documented in the medical records. The study PI and study engineers will be trained in Medical Device Reporting principles.

The study will only last 144 hours. No follow up visits or tests are required.

This device is considered a non-significant risk device requiring no IDE.

7. Study Statistics

a. Primary outcome variable.

- Mean elapsed time needed to re-establish SpO2 within the desired range after an alarm. Does the computer do a better job of keeping the patient in the desired saturation level range compared to the current manual mode? Does the patient return to the prescribed saturation level range quicker in the automatic mode compared to the manual mode?

b. Secondary outcome variables.

- Proportion of time SpO2 is within the prescribed range computed using an area-under-the-curve approach. Is our device safe to use on neonates? Is the transition from automatic to manual mode smooth? Does the device respond appropriately to the patient's saturation level?
- Does the frequency of acute events (apnea, bradycardia and/or desaturation events) decrease if the oxygen saturation level is kept under better control?

- c. Our goal is to enroll 60 patients into the study. We expect to consent 70 subjects to account for drop-out.

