- d. Our pilot study of 6 patients demonstrated that when the device was in the automatic mode, the patient spent more time within the prescribed oxygen saturation goals and that it took less time for them to return to the prescribed oxygen saturation range whenever they were outside of the range. Even though this wasn't considered statistically significant, we felt that this was due to the fact the infants were only on the device for 12 hours (two 3-hour periods of automatic control and two 3-hour periods of manual control). This pilot study did show a significant decrease in the number of bradycardia events while the infants were in the automatic mode. With our current study, the patients will be on the device for 6 days so a total of 72 hours of automatic control and 72 hours of manual control, so we are hoping to find statistical significance in all our study metrics.
- e. If the healthcare team determines that the patient's respiratory distress is worsening and he/she needs more support than can be provided by the high flow nasal cannula or bubble CPAP, the study will be terminated, and the patient will be placed on whatever device the healthcare team chooses. On the other hand, if the healthcare team determines that the infant is doing well enough that they no longer need the high flow nasal cannula or bubble CPAP, we will stop the study and allow the infant to be taken off the respiratory device.

8. Risks

- a. The study high flow nasal cannula device and bubble CPAP device are the same exact set ups we currently use in the NICU except that there is a computer attached to the oxygen blender that can automatically adjust the FiO2 being delivered to the patient. A member of the research team will be at the baby's bedside to make sure it is operating properly for the first 12 hours and then daily for 1 hour to make sure everything is functioning appropriately. They will also be available by phone for the entire time the infant is on the device.

The bedside nurse and respiratory therapist will be educated on how the device works and what to do if they have any questions. A two-page information sheet will be hanging from the device, so they have a reference to look at. This information sheet includes a frequently asked questions section. It also reminds them to call the study team for any questions.

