Cover Page

NCT04269161

NICU Oxygen Control Study

Statistical Analysis Plan

October 21, 2024

Statistical Design and Power

A crossover design was chosen because premature infants should have fewer events as they grow older each day, and a crossover design will mitigate this potential confounding effect. Furthermore, because every subject receives the device and the standard of care (nurse only), every subject serves as their own perfectly matched control. All subject-specific effects cancel out, so there is no concern for covariate imbalance. Finally, selection bias is minimized because all subjects receive all “treatments”. Nonetheless, the concealed allocation will be used with blocked randomization at each site, using sealed envelopes. The subjects will be randomized to group A or B in sets of 8 (i.e. in each group of 8 envelopes, 4 will be group A and 4 will be group B). During the entire study process the infants will receive normal NICU care and the parameters the SpO_2 range will be set by the physician caring for the infant. There are also built in manual overrides for the device, which allow the NICU staff to make changes while the subject is on the device phase of the study. The device will be able to record these changes and the staff will record their manual interventions in the study diary.

We have planned our sample size using a non-inferiority test for a 24 period, 2 treatment cross-over design, based on our primary endpoint, t_Δ . For a given patient, define $t_\Delta = (\text{mean elapsed time needed for device to re-establish } \text{SpO}_2 \text{ after alarm}) - (\text{mean elapsed time needed for nurse to re-establish } \text{SpO}_2 \text{ after alarm})$. The margin of non-inferiority will be chosen as $t_\Delta > -10 \text{ sec}$, so that a device which is no worse than 10 sec, on average than a nurse will be considered non-inferior. Assuming the standard deviation of $t_\Delta = 12$ and the true mean difference is zero under the alternate hypothesis, a sample size of 48 achieves 88% with $\alpha=0.05$. If there is 16% patient drop-out before crossover, so that the final $n=40$, the power drops to 82%. In all analysis, a (paired) t-test will be used. Our secondary endpoint will be analyzed in a similar manner. The secondary endpoint is the proportion of time SpO_2 is within the prescribed range, using an area-under-the-curve approach (with a discrete state) to account for varying time-on-test.

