We will plan for one interim analysis to determine if the trial should be stopped early due to futility (strong evidence of inferiority, where a confidence interval for t_Δ lies entirely to the left of -10 and doesn't intersect -10) or for efficacy (strong evidence of superiority with margin $> +20 \text{ sec}$). This will be carried out when $n=32$ (16 subjects per site) is attained and stopping decisions will be based on O'Brien-Fleming stopping principles. The interim analysis will be carried out by an independent statistician on the University of Missouri's Data Safety and Monitoring Committee, which is also available to monitor the study for adverse events if requested by the IRB. In the event that the patient drop-out is greater than 16% before crossover, then a more complicated estimation procedure will be employed using mixed effects models; otherwise, complete cases will be used.

Assuming that the probability of enrollment for a given NICU patient is 10% (conservative est.), and because there are ≥ 6 new NICU patients/week at each hospital, we expect to enroll 48 patients and collect data in 43 weeks (11 months).

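### The SAP defines t_Δ as device minus nurse, but its non-inferiority and futility rules only work for nurse minus device: read literally, a slower device passes and one 10 sec or more faster fails

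*SAP*

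**What the plan says.** All the rules are in the SAP, Statistical Design and Power.

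- **Definition.** For each patient, t_Δ is the "mean elapsed time needed for device to re-establish" SpO2 after an alarm, minus the same quantity for the nurse.
- **Margin.** "The margin of non-inferiority will be chosen as" t_Δ > -10 sec, followed at once by the explanation "so that a device which is no worse than 10 sec, on average than a nurse will be considered non-inferior".
- **Interim futility.** Strong evidence of inferiority is a confidence interval for t_Δ that "lies entirely to the left of -10".
- **Interim efficacy.** The criterion is "strong evidence of superiority with margin" above +20 sec. This clause does not name t_Δ.

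The protocol does not use the symbol t_Δ, but it fixes the direction of benefit. Section 7a asks: "Does the patient return to the prescribed saturation level range quicker in the automatic mode compared to the manual mode". Section 7d reports that in the six-patient pilot, in automatic mode, "it took less time for them to return to the prescribed oxygen saturation range whenever they were outside of the range", and adds that the result was not statistically significant.

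**The concern.** The endpoint is a time to recovery, so less is better. With device minus nurse, a device 10 sec slower has t_Δ = +10 and a device 10 sec faster has t_Δ = -10. A tolerance of 10 sec on the slow side is therefore t_Δ < +10. The SAP's inequality puts no upper limit on how slow the device may be and excludes devices that are much faster. The futility rule repeats the reversal by calling an interval that shows the device more than 10 sec faster evidence of inferiority.

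The symbols and the words of the primary decision rule thus give opposite answers. Someone who follows the words decides correctly. Someone who programs the symbols does not, and the SAP gives the interim analysis to an independent statistician, who has to rely on the text. The conflict also lies on the side where the investigators hope to find the result: a faster device is a negative t_Δ as defined. If the sign is settled only once results are known, the direction of the primary test was not clearly prespecified.

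**Working it through.** **Inputs (SAP).** SD of t_Δ 12 sec; margin 10 sec; true difference 0 under the alternative; n = 48 (40 after drop-out); α = 0.05; paired t-test; interim at n = 32. The SAP does not say whether α is one- or two-sided, and it gives no numeric interim boundary. I take one-sided 0.05 because it is the level that reproduces the stated power.

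**1. Direction of each rule**

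| Rule | On the written scale (device − nurse) | On nurse − device |
|---|---|---|
| Non-inferior: t_Δ > -10 | device less than 10 sec *faster*, or slower by any amount | device less than 10 sec slower, as the words say |
| Futility: interval wholly below -10 | device more than 10 sec *faster* | device more than 10 sec slower, as the words say |
| Efficacy: > +20, if on the t_Δ scale | device more than 20 sec *slower* | device more than 20 sec faster |

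The rules fit nurse minus device and contradict the definition as written.

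**2. Reproducing the stated power (88% and 82%)**

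- Paired test as named, SE = 12/√48 = 1.73: power at zero difference is above 0.999, which does not match.
- Two-group standard error, SE = 12·√(2/24) = 3.46: noncentral-t power is 0.885 at n = 48 and, with SE = 12·√(2/20) = 3.79, 0.827 at n = 40. Both match.

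Which variance was intended is a separate question, so I carry both. Correcting the sign leaves these figures alone: at a true difference of 0 the distance to the margin is 10 sec for either -10 or +10.

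**3. Final test, n = 48**

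Probability of declaring non-inferiority at true mean μ = E(t_Δ), device minus nurse, from the noncentral t with noncentrality (μ + 10)/SE for the rule as written and (10 − μ)/SE with the sign corrected. Degrees of freedom are 47 (paired) and 46 (two-group).

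| True effect | μ | As written, SE 1.73 | As written, SE 3.46 | Corrected, SE 1.73 | Corrected, SE 3.46 |
|---|---|---|---|---|---|
| 15 sec slower | +15 | 1.00 | 1.00 | 0.00 | 0.001 |
| 10 sec slower | +10 | 1.00 | 1.00 | 0.05 | 0.05 |
| Equal | 0 | 1.00 | 0.88 | 1.00 | 0.88 |
| 5 sec faster | -5 | 0.88 | 0.41 | 1.00 | 1.00 |
| 8 sec faster | -8 | 0.31 | 0.14 | 1.00 | 1.00 |
| 10 sec faster | -10 | 0.05 | 0.05 | 1.00 | 1.00 |
| 15 sec faster | -15 | 0.00 | 0.001 | 1.00 | 1.00 |

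Example: at μ = -8 with SE 1.73, the noncentrality is 2/1.73 = 1.15 against a critical value of 1.68, which gives 0.31.

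At one-sided 0.025 with SE 1.73, devices 5, 8 and 10 sec faster pass with probability 0.81, 0.20 and 0.025. At n = 40 (one-sided 0.05) the ±15 sec results are 1.00 for the slower device and at most 0.002 for the faster one, under both variances.

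**4. Interim, n = 32**

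The probability that the interval lies wholly below -10 is Φ((-10 − μ)/SE − z). For μ = -20 the first term is 10/SE.

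- SE = 12/√32 = 2.12: Φ(4.71 − 1.96) = 0.997; Φ(4.71 − 2.5) = 0.99.
- SE = 12·√(2/16) = 4.24: Φ(2.36 − 1.96) = 0.65; Φ(2.36 − 2.5) = 0.44.

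The range z = 1.96 to 2.5 covers the O'Brien-Fleming values computed at information 32/48: 2.09 (one-sided 0.05) and 2.45 (one-sided 0.025). A device truly 20 sec *slower* (μ = +20) is stopped with probability 0.00 in every case.

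**The case against.** The best defence is that the intent is plain. The words beside the inequality state the rule correctly, the futility clause is labelled as inferiority, and only the order of two terms in the definition disagrees. Any competent analyst would notice, so the harm needs someone to follow the symbols and ignore the sentence beside them. The probabilities also look worst at true differences of 10 to 20 sec. The SAP plans for zero, where both versions of the rule behave alike, and no document gives a pilot effect in seconds. The pilot had six patients and its result was not significant.

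Much of this stands. It is one slip, the words lead to the right decision, the design and power are untouched, and a faster device is a hope with no stated size. The efficacy clause does not name t_Δ, so it is better called ambiguous than wrong.

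The conflict itself remains. The definition is spelled out in words with an explicit minus sign, -10 appears in two separate rules, the futility rule gives its direction in words, and no other part of either document repairs it. Smaller benefits are affected too: with SD 12, a device truly 8 sec faster passes only 31% of the time under the written rule. A primary decision rule should not depend on the reader choosing the words over the formula.

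**Conclusion.** The concern holds. As written, the non-inferiority criterion and the futility rule contradict the definition of t_Δ and the SAP's own explanation of them. Followed literally, a slower device passes at least 88% of the time at n = 48, and a device 10 sec or more faster passes at most 5% of the time. A device 20 sec faster would be stopped at the interim as inferior with probability about 0.99 (SE 2.12) or 0.44 to 0.65 (SE 4.24). These figures assume one-sided 0.05 at the final analysis and interim critical values between 1.96 and 2.5. The direction of the error depends on neither the assumed levels nor the choice of variance. Sample size and stated power do not change. Because this is the primary decision rule and a stopping rule, it must be corrected, even though the intent can be inferred.

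**What to change.** **Simplest.** Redefine t_Δ as nurse time minus device time. Keep -10 for non-inferiority and the futility wording, and state that +20 sec is on that scale.

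**Alternative.** Keep device minus nurse and write: non-inferior if the upper one-sided confidence limit for t_Δ is below +10 sec; futility if the interval lies wholly above +10; superiority for t_Δ beyond -20.

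Either way, tie the efficacy criterion to t_Δ by name and say whether the estimate or a confidence limit is compared with it, since the SAP specifies an interval only for futility. One sentence giving the meaning of a positive value would prevent a recurrence.

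Make the change before any comparison of the two modes is run. If the interim analysis has already taken place, record which sign convention it used.

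**Cost.** SAP wording only: two terms swapped in one definition and one clause added. Sample size, data collection and conduct are unaffected.

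### The SAP's stated power (88% at n=48, 82% at n=40) does not follow from its own inputs, which give more than 99.9% at both sizes

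*SAP*

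**What the plan says.** The SAP, under Statistical Design and Power, sizes the trial with a "non-inferiority test for a 24 period, 2 treatment cross-over design". All the inputs are in the same paragraph:

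- The endpoint t_delta is introduced with "For a given patient, define" and is that infant's mean recovery time after an alarm on the device minus the same mean under nurse control. It is one within-infant difference per infant.
- The standard deviation is 12, attached to t_delta itself. No unit is given; seconds are assumed here, as for the margin.
- The margin is 10 seconds, and the "true mean difference is zero under the alternate hypothesis".
- Alpha is 0.05, with no statement of one- or two-sided.
- The test: "In all analysis, a (paired) t-test will be used".

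From these the SAP concludes that "a sample size of 48 achieves 88% with" that alpha, and that with 16% drop-out and 40 infants left "the power drops to 82" per cent. Protocol section 7, item c, has a different target: "Our goal is to enroll 60 patients into the study". Neither document gives a power for 60.

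**The concern.** A margin of 10 seconds against an SD of 12 for a paired difference is a large standardised distance (10/12 = 0.83), and 48 pairs should detect it almost with certainty. A stated power of 88% is far too low for those inputs, so either an input or the result is wrong.

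This is the SAP's only quantitative justification for the number of infants, and it concerns the primary endpoint. As it stands, a reader cannot tell what variability the trial was planned for. If the true planning SD is about twice the one printed, the confidence interval for t_delta will be about twice as wide as the text implies, against a margin of only 10 seconds.

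**Working it through.** **Inputs** (all from the SAP, Statistical Design and Power): SD of t_delta s = 12; margin 10; true difference 0; n = 48, and n = 40 after drop-out (48 × 0.84 = 40.3); paired t-test. Because sidedness is not stated, both one-sided 0.05 and one-sided 0.025 are run.

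**Formula.** For a paired non-inferiority t-test, power is the probability that a noncentral t variable with n − 1 degrees of freedom and noncentrality 10/(s/√n) exceeds the one-sided critical value of the central t.

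**Attempt to reproduce the stated 88% and 82%**

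- n = 48: standard error 12/√48 = 1.73; noncentrality 10/1.73 = 5.77; critical value 1.68 (one-sided 0.05) or 2.01 (one-sided 0.025). Power 99.997% or 99.99%.
- n = 40: standard error 12/√40 = 1.90; noncentrality 5.27; critical value 1.68 or 2.02. Power 99.98% or 99.93%.

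Neither printed figure is reproduced. With these inputs 88% power is reached at n = 13 (one-sided 0.05) or n = 17 (one-sided 0.025).

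**Could 12 be the SD within each mode?** Then the SD of t_delta is 12 × √(2(1 − r)), where r is the within-infant correlation between modes. At r = 0 it is 16.97, and power at n = 48 / 40 is 99.1% / 97.8% (one-sided 0.05) or 97.9% / 95.3% (one-sided 0.025). Any positive r raises these, and at r = 0.5 the SD is 12 again. Reaching an SD of 24 would need r = −1. This reading does not recover the stated figures.

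**What would give roughly 88% and 82%?** These are back-calculations; the documents do not say how the figures were obtained.

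1. Two independent groups of 24 (or 20), SD 12, one-sided 0.05. Noncentrality 10/(12 × √(2/24)) = 2.89 gives 88.5%; 10/(12 × √(2/20)) = 2.64 gives 82.7%. Close, though the second rounds to 83%.
2. A paired test at one-sided 0.05 with an SD of t_delta between 24.09 and 24.43. Both powers round to the printed values.
3. A paired test at one-sided 0.025 with an SD between 21.47 and 21.59. Both powers again round to the printed values; at 21.5 they are 88.4% and 81.8%.

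Since 2 and 3 fit equally well, the printed powers identify neither the SD nor the sidedness.

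**Power (%) of the paired t-test, margin 10, true difference 0**

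| SD of t_delta | One-sided alpha | n=40 | n=48 | n=60 |
|---|---|---|---|---|
| 12 | 0.05 | 99.98 | 99.997 | >99.99 |
| 12 | 0.025 | 99.93 | 99.99 | >99.99 |
| 16.97 | 0.05 | 97.8 | 99.1 | 99.8 |
| 16.97 | 0.025 | 95.3 | 97.9 | 99.4 |
| 21.5 | 0.05 | 89.3 | 93.7 | 97.2 |
| 21.5 | 0.025 | 81.8 | 88.4 | 94.3 |
| 24 | 0.05 | 82.7 | 88.5 | 93.9 |
| 24 | 0.025 | 72.9 | 80.7 | 88.8 |

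**Precision.** The 95% interval half-width at n = 48 is 2.01 × SD/√48: 3.5 seconds for SD 12, 6.2 for SD 21.5 and 7.0 for SD 24.

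**The case against.** The strongest reply is that the error, taken at face value, is conservative: if SD 12 is right, the trial has more power than it claims and nothing about its conduct changes. Even the least favourable row in the table, SD 24 at one-sided 0.025, gives 88.8% at the Protocol's goal of 60. That row also cannot explain the SAP, since it yields 80.7% and 72.9% rather than the printed figures. The SDs of 21.5 and 24 appear nowhere in the documents.

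Much of this stands. No scenario examined calls for more infants or a different design, and the back-calculated SDs are diagnostic only; they are not candidates to adopt because they preserve a printed number. Nor can 60 be relied on for reassurance, because the SAP plans and powers for 48. None of it makes 88% and 82% correct.

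Two other explanations fail. The O'Brien-Fleming interim look at n = 32 is not part of the stated calculation, and it could not plausibly take power from above 99.9% to 88%. The sign of the margin is questionable (t_delta is device minus nurse, yet non-inferiority is written as above −10), but with a true difference of zero the power is the same in either direction.

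**Conclusion.** The concern holds. On the SAP's own inputs, power is above 99.9% at both 48 and 40 infants, not 88% and 82%, for either reading of alpha. Treating 12 as a per-mode SD still leaves at least 95.3% at zero or positive within-infant correlation. The calculation assumes a fixed sample, one t_delta per infant, approximate normality, and the SD in seconds.

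Whether the SD or the power is the wrong number cannot be determined from the documents. The two possibilities point in opposite directions: a trial with more power than stated, or one planned for about twice the written variability. The error should be corrected because it leaves the sample-size rationale unverifiable; by itself it does not endanger the trial.

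**What to change.** Keep the sample size and the paired test. In the SAP's power paragraph:

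- State whether alpha 0.05 is one-sided or two-sided.
- State what the 12 measures, its unit and its source. The six-patient pilot in Protocol section 7, item d, is an obvious place to look, though the documents do not report its variability.
- Then correct whichever figure is wrong:
  - If 12 is the SD of t_delta, replace the powers with above 99.9% at n = 48 and n = 40.
  - If 12 is the SD within each mode, state the assumed within-infant correlation and recompute (99.1% and 97.8% at zero correlation, one-sided 0.05).
  - If the intended SD of t_delta is larger, state it, justify it from data and recompute. It should not be chosen to reproduce 88% and 82%.
  - If two independent groups were used, replace that calculation with the paired one.
- Say that the power is for a fixed sample and ignores the interim look.
- Give the power at n = 60 as well, or reconcile 48 with the Protocol's goal of 60.

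The cost is a short recalculation and revised SAP wording, with no additional infants and no change to the design.

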- i. We will continuously download the vital signs and pulse oximeter data from the monitor system for up to 24 hours prior to the study as well as throughout the study to see how well the healthcare providers kept the baby in the desired range during that time period.

- Continuously measure SpO2 using existing sensors in the NICU. A pulse oximetry unit will be used to continuously gather SpO2 data from the patients.
- Continuously measure heart rate using existing sensors in the NICU. A cardiorespiratory monitor will be used to continuously gather heart rate data from the patients.
- Continuously measure respiratory rate using existing sensors in the NICU. A cardiorespiratory monitor will be used to continuously gather respiratory rate data from the patients.
- Continuously measure FiO2 concentration. The computer system attached to the research device, will continuously keep track of the infant's SpO2, heart rate, respiratory rate and FiO2 being provided to the patient. This data will be downloaded and analyzed by the study personnel once the device is removed from the patient.

j. When the device is set on the manual mode, the healthcare providers will be responsible for adjusting the oxygen concentration to keep the infant in the desired saturation range set by the primary healthcare team.

k. When the device is set in the automatic mode, the computer will make the necessary adjustments to the oxygen concentration to keep the infant in the desired saturation range. The computer will strive to keep the oxygen saturation level at the median of the range set by the primary healthcare team.

l. The infant will be placed in one of these modes for 6 hours and then switched to the other mode for the next 6 hours. Ideally this will occur every 6 hours +/- 1 hour.

m. This cycle will be repeated for the next 132 hours (5.5 days) except at 48 and at 96 hours where it will be kept on the same mode for at 12- hour period in order to switch the time of day the infant is on automatic mode so it not always the same time of day for the full 6 days.

n. Infants will be randomized so some will start in the automatic mode (A) while others start in the manual mode (B). Due to concern that the time of day may play a role in the variation in the patient's oxygen need and/or the frequency of acute events, the patients will be randomly assigned to one of two tracks:

- ABAB/ABAB/BABA/BABA/ABAB/ABAB
- BABA/BABA/ABAB/ABAB/BABA/BABA

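### The pooled paired t-test leaves out the randomised track, so any odd-versus-even slot difference adds avoidable noise and, if the tracks finish unequal, a small bias

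*SAP*

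**What the plan says.** The SAP (Statistical Design and Power) fixes the method in one sentence: "In all analysis, a (paired) t-test will be used". The secondary endpoint is to be handled in a similar way. No term for track, period, clock time or site is named. The only departure is a mixed model with unspecified terms, used if drop-out before crossover exceeds 16%; otherwise complete cases are analysed.

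The protocol (section 4, item n) gives the reason for two tracks: "Due to concern that the time of day may play a role in the variation". The first track is "ABAB/ABAB/BABA/BABA/ABAB/ABAB", where A is automatic and B is manual; the second is its exact mirror. Item m explains that a mode is held for 12 hours at 48 and 96 hours to change the time of day at which automatic mode runs. On period length, item l says "Ideally this will occur every 6 hours +/- 1 hour". No clock start time is fixed.

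On allocation, the SAP says that "the concealed allocation will be used with blocked randomization at each site" and that "in each group of 8 envelopes, 4 will be group A and 4 will be group B". I take the SAP's groups A and B to be the protocol's two tracks.

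**The concern.** The design guards against a time-of-day effect that the analysis then ignores. If automatic mode does not fall equally on all daily slots within a track, part of any slot effect enters each infant's t_delta, with one sign in one track and the opposite sign in the other. A pooled paired t-test counts that known, removable difference as random error. The mirror image protects the mean only if the two tracks contribute equal numbers and equal stays. At stake are the width of the interval that decides non-inferiority and, when the tracks are unequal, the position of the estimate.

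**Working it through.** **Inputs.** From the SAP: n = 48, or 40 after drop-out; SD of t_delta 12 (read as seconds); true difference 0; margin 10 sec, taken in its verbal sense; alpha 0.05; blocks of 8 within site. From the protocol: the two 24-period tracks and the 6-hour periods. Assumed: d, the mean of slots 1 and 3 minus the mean of slots 2 and 4, because the documents give no value (5, 10 and 20 sec shown); 12 as the within-track SD; equal weight per period; similar clock start times.

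**1. The plan's own power.** The stated 88% and 82% are reproduced by a one-sided 0.05 two-group t formula: SE = 12 × √(4/n) = 3.46 (n = 48) and 3.79 (n = 40), giving 88.5% and 82.7%. The paired t-test that the SAP names has SE = 12/√n = 1.73 and 1.90, giving 99.997% and 99.98%. A paired test would give about 88% only with an SD near 24.

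**2. Slot count.** In the first track, automatic mode falls on 4, 2, 4 and 2 of the 6 days in slots 1 to 4: odd slots 8 of 12, even slots 4 of 12. The share of automatic periods in odd slots minus the share of manual periods in odd slots is 8/12 − 4/12 = 1/3. The second track gives −1/3. By length of stay the figure is:

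| Hours completed | 24 | 48 | 72 | 96 | 120 | 144 |
|---|---|---|---|---|---|---|
| Contrast (× d) | ±1 | ±1 | ±0.33 | 0 | ±0.20 | ±0.33 |

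**3. Which effects survive.** Slots 1 and 3 lie 12 hours apart, as do slots 2 and 4. A 12-hour day/night step and a 24-hour sine wave, run through the track at several start hours, both gave an automatic-minus-manual imbalance of zero. Only the odd-versus-even contrast remains. A single slot that differs by x gives d = x/2, and so shifts t_delta by x/6.

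**4. Equal tracks, n = 48.** Pooled SD = √(144 + (d/3)² × 48/47).

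| d (sec) | SD | SE = SD/√48 | Widening |
|---|---|---|---|
| 5 | 12.12 | 1.75 | 1% |
| 10 | 12.46 | 1.80 | 4% |
| 20 | 13.76 | 1.99 | 15% |

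Simulated type I error at the margin for d = 20 is about 3% instead of 5%. Paired power is still 99.95%.

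**5. Unequal completers.** Shift = (n1 − n2)/n × d/3. At 22:18 and d = 20 this is (4/40) × 6.67 = 0.67 sec. Simulated type I error is about 6% when the imbalance favours the device; it falls below 5% when it runs the other way. If 8 infants are lost at random from 24:24, the gap is 4 or more with probability about 25%, 6 or more about 5%, and 8 (24:16) about 0.4%.

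**6. With a track term.** The intercept is the mean of the two track means, with SE = (12/2) × √(1/n1 + 1/n2): 1.73 at 24:24 and 1.91 at 22:18. For full-course infants the bias is zero and simulated type I error is about 5% in both cases.

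**7. Early leavers.** Suppose one track all finish and a quarter of the other stop by 48 hours. The track means carry +d/3 and −(0.75 × d/3 + 0.25 × d) = −d/2. Their average is −d/12, or 1.67 sec in size at d = 20. A single track term does not remove this.

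**The case against.** The strongest reply is that little depends on this. Ordinary circadian and day/night effects are balanced within each track. Slots run from device start, so if start times vary at random the tracks do not line up with the clock: simulation then shows no bias even with unequal tracks, and a track term does not shrink the standard error. A d of 20 sec needs one slot to differ by 40 sec, which is large beside an SD of 12 and a margin of 10. The SD of 12 is given for t_delta itself and may already contain the track component. Blocks of 8 give exact balance at 24 per site, and at the interim with 16 per site. All of this stands, and it limits the size of the point.

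Some of the problem remains. An influence that recurs every 12 hours does not cancel; staff handover would be one if shifts last 12 hours, which the documents do not say. The planned mixed model does not close the gap: it is triggered only by drop-out before crossover, so infants who switch modes and then leave early do not count towards it, and its terms are not given.

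A reader might infer three stronger things. One is that time-of-day effects in general inflate or bias the result; the 12-hour spacing rules that out. Another is that leaving out site biases the result; site main effects cancel within the infant, and only a site-by-mode interaction would matter. The third is that the non-inferiority decision is in danger; at a paired SD of 12 it is not.

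**Conclusion.** The point holds as a modest matter of precision and robustness. For full-course infants the omitted track term matters only through an odd-versus-even slot difference and only if start times are similar. With equal tracks the error is conservative. With plausible imbalance the shift is a fraction of a second to about one second, against a 10-sec margin. Early leavers are the weaker spot, because those who stop by 48 hours carry the whole of d. The sizes rest on assumed values of d, on 12 being the within-track SD, and on equal weight per period. Because t_delta averages over alarms, uneven alarm counts could disturb the cancellation. If the paired SD were nearer 24, the widening at d = 20 would be smaller, about 4% (√(1 + 45.4/24²) = 1.04), but there would be less spare power to absorb it.

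**What to change.** Replace the pooled test by a regression of t_delta on randomised track (coded +1/2 and −1/2), and test the intercept against the margin. Centred site may be added to match the blocked allocation, but it is optional.

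Also pre-specify a period-level mixed model with mode, actual clock slot from the device time stamps, study day and a random infant effect. Use it whenever stays differ, not only when drop-out before crossover exceeds 16%. The clock-slot term also deals with start times that vary between infants.

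Analyse the secondary endpoint in the same way. The schedule does not change. The cost is SAP wording and a few degrees of freedom; at 22:18 the track term raises the standard error from 1.90 to 1.91 sec if no slot effect exists.
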